- *Reduced neurological disability at hospital discharge (Aim 2)*
- *Reduced neuropsychological and functional deficits among survivors at 180 days (Aim 3)*

D.1.2. Overview

Design: Prospective protocol implementation study with an observational comparison group [REOX II (intervention component) versus REOX I (observational component)]

Participants: Adult patients resuscitated from cardiac arrest

Enrollment location: Emergency Departments of 6 urban academic medical centers

Intervention: Implementation of a clinical protocol for rapid FiO₂ optimization after ROSC from cardiac arrest.

Primary outcome: Good neurological outcome (defined as Modified Rankin Scale ≤ 3 ⁴⁵ at hospital discharge).

Secondary outcomes: Neuropsychological tests and ability to return to work among survivors at 180 days.

Mechanistic outcomes: Oxidative stress markers (IsoPs/IsoFs) in plasma 0-6 hours after ROSC.

Estimated sample size and study duration: 280 patients (205 from REOX I and 75 from REOX II).

[figure not shown]
D.2. REOX II Study Protocol

Study setting and population: This study is the second phase in a two-phase study. The initial phase, REOX I, was an observational-only study. As in REOX I, REOX II will identify subjects with return of spontaneous circulation (ROSC) after cardiac arrest in 6 hospitals (Cooper University Hospital, Camden, NJ; Hospital of the University of Pennsylvania and Penn-Presbyterian Medical Center, both in Philadelphia, PA; University of Mississippi Medical Center, Jackson, MS; Methodist Hospital, Indianapolis, IN; and Beth Israel Deaconess Medical Center, Boston, MA). The inclusion criteria are: age > 17 years; cardiac arrest; ROSC achieved; comatose (Glasgow Coma Scale motor score < 6) after ROSC; and clinician intent to treat with target temperature management. The exclusion criteria are: presumed etiology of arrest is trauma, hemorrhage or sepsis; resident of a nursing home or other long-term care facility; known or clinically apparent pregnancy; known lack of commitment to aggressive support by next of kin; and any other condition, that, in the opinion of the investigator, would preclude the subject from being a suitable candidate (e.g. end stage chronic illness with no reasonable expectation of survival to hospital discharge).

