Patient identification and recruitment: Each of the participating centers currently has a mechanism in place for real-time notification of study personnel when an OHCA subject arrives in the emergency department (ED) or when a cardiac arrest occurs in-hospital. Each center has previously validated its notification mechanism to ensure that subjects will not be missed and the population of potentially eligible subjects will be consecutive cardiac arrest subjects. Study personnel will assess patient eligibility and will immediately enroll subjects meeting all inclusion and no exclusion criteria.

Informed consent: In line with REOX I (observational-only component), in REOX II we will begin initial collection of cardiac arrest and post-resuscitation data immediately after ROSC. As per the inclusion criteria all subjects will be comatose during the initial post-ROSC period and therefore will not be able to consent themselves for the study intervention (i.e. protocol for rapid FiO₂ optimization after cardiac arrest). Once a subject is identified to have all inclusion and no exclusion criteria, we will approach surrogates (i.e. next of kin or legally authorized representative)

Figure 9 Flow diagram for enrollment

[figure not shown]
within the first four hours after ROSC for written informed consent and HIPAA authorization prior to implementation of the study intervention. If communication with a surrogate within the first four hours after ROSC is not achieved the subject will not be eligible for the study intervention. However, for subjects who are excluded from the study intervention due to lack of informed consent within the first four hours after ROSC, we will approach subjects or surrogates at a later time for written informed consent and HIPAA authorization for participation in the observational only (REOX I) component of the study including (a) use of plasma samples for research purposes (both stored samples obtained at the time of initial resuscitation and new samples); (b) determination of Modified Rankin Scale at hospital discharge; and (c) follow-up visits for neuropsychological testing at 180 days (**Figure 9**).

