Therapeutic interventions: **Table 3** displays the standard elements of post-resuscitation care across all centers. All sites are experienced in target temperature management after ROSC and target 32-36°C for 24 hours using external cooling devices (Arctic Sun, Medivance, USA, or Gaymar III, Gaymar Industries, USA). Using a standardized order set for target temperature management induction, we demonstrated successful achievement of target temperature in 96% of patients and a median time from ROSC to target temperature of four hours (i.e. faster than the landmark randomized trial) in our routine clinical care.⁴⁰ All standard elements in **Table 3** reflect current AHA recommendations.¹² All subjects in this study will receive standard post-resuscitation care. Since none of the sites previously had a protocol in place for FiO₂ titration after ROSC and our standardized order sets for post-resuscitation care do not have orders for FiO₂ titration, subjects in REOX I (observational only component) had clinician-directed FiO₂ titration after ROSC.

For the interventional component of this study we will implement the protocol for rapid FiO₂ optimization after cardiac arrest (**Figure 10**) at all sites. Once a subject is identified and written informed consent is obtained from a surrogate, the study intervention (i.e. rapid FiO₂ optimization protocol) will be activated by the investigator who receives notification in real-time. (see “*Patient identification and recruitment*” above). The on call investigator will communicate directly with the clinical care team at the bedside and will ensure activation and adherence to the clinical protocol. Subjects enrolled in the study intervention will receive standard post-resuscitation care in **Table 3** *plus* rapid FiO₂ optimization according to **Figure 10**. Our sites have an outstanding track record of sustained clinical adherence to new resuscitation protocols for multi-year time periods.³⁷⁻⁴² Subjects who are excluded from the study intervention due to lack of informed consent within the first four hours after ROSC, will still be eligible for the observational only aspect of this study (REOX I). These subjects will receive standard post-resuscitation care outlined in **Table 3**, but will not have activation of the rapid FiO₂ optimization.

Table 3: Standard elements of post-cardiac arrest care across all centers. (TH = therapeutic hypothermia; GCS = Glasgow Coma Scale; ROSC = return of spontaneous circulation)

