Standard care elements
24/7 capability for interventional cardiac catheterization (if needed)
Standardized patient selection for TH (i.e. GCS motor <6 after ROSC)
Target temperature goal for TH of 32-36°C
Maintain TH target temperature 24 hours
Controlled rewarming to avoid hyperpyrexia after TH completion
24/7 capability for goal-directed hemodynamic support interventions
24/7 capability for continuous electroencephalographic monitoring
Evidence-based approach to neurological prognostication (e.g. wait ≥72 hours after ROSC before support limitations for poor neurological prognosis)

Instead these patients will have clinician-directed FiO_2 titration after ROSC. Data will be prospectively collected on these patients (see “*Data Collection*” below) and we will approach subjects or surrogates at a later time for written informed consent and HIPAA authorization for participation in the observational component of the study.

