Secondary analyses: We will compare proportions of good neurological outcome [defined as a mRS ≤ 3 (based on the preliminary data of our collaborator, [name], University of Pittsburgh)],⁴⁵ between subjects who receive the study intervention (i.e. rapid FiO₂ optimization) vs. those who do not receive the study intervention, using binomial test. Among survivors, we will compare the 180-day neuropsychological measures (composite z-scores for each cognitive domain) between the same two groups using t-test or Mann-Whitney U as appropriate with corrections for multiple comparisons. We will compare the proportions of patients able to return to work between the two groups using binomial test. We will compare plasma IsoPs/IsoFs at each time point between the two groups using t-test or Mann-Whitney U as appropriate with corrections for multiple comparisons.

Sample Size: The sample size calculation in the initial study proposal was based on the primary outcome, mRS at hospital discharge, and we planned to enroll a total of 266 subjects. To ensure adequate power to test the relationships between the above independent variables and cognitive domains, we assumed a medium relationship strength between the six independent variables and each of the five cognitive domains ($R^2 = 0.15$). In order to achieve 80% power and an $\alpha = 0.05$ we would require a minimal of 85 subjects to undergo neuropsychological testing at 180 days. This sample size will be among the largest prospective studies of

neuropsychological outcomes that we are aware of in the literature.^{8,29-32} Assuming a 15% drop out rate for lost to follow up for neuropsychological testing at 180 days we would require 98 subjects to be discharged with a mRS \leq 4. Based on preliminary data from REOX I we expect 35% of patients will be discharged with a mRS \leq 4 and undergo cognitive testing at 180 days. We would therefore require a minimal total sample size of 280 subjects between REOX I and II combined for the multivariable testing. We have enrolled 200 subjects in REOX I to date. We anticipate additional subjects to be enrolled in REOX I and therefore plan for 75 subjects to be enrolled in REOX II to ensure a total sample size of at least 280 subjects.

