Overview of the safety monitoring plan and serious adverse event tracking: In order to help ensure adequate protection of human subjects enrolled in this clinical study, we established an independent three-member **Data Safety Monitoring Board (DSMB)** (see **DSMB Charter**). The Chair of the DSMB will be [name]. [name] is an established investigator and is currently the Director of Clinical Research, Department of Emergency Medicine, Cooper University Hospital, Camden, NJ. The DSMB will be charged with reviewing all serious adverse event reports and will also perform interim analysis of the data after one-third (n=25) and two-thirds (n=50) of the patients have been enrolled in REOX II. Given neither REOX I nor REOX II are blinded, all data reviewed by the DSMB will be unmasked. At both interim analyses the committee will be asked to render a decision as to whether the trial should be continued, modified, or stopped based on the safety profile of the interim data. We have defined the following *a priori* as a reportable serious adverse event (SAE): (1) any events resulting in death or repeat cardiac arrest; (2) sustained hypoxia (defined as $\text{SaO}_2 < 88\%$ for more than three consecutive minutes); (3) heart rate < 50 for greater than one minute; (4) documented cyanosis at any time; or (5) withdrawal of a subject from the trial for any reason. We will define excessive rates of any single SAE *a priori* as a $>15\%$ difference in the prevalence (% of total number in each group) between the two groups [i.e. subjects who receive the study intervention (i.e. rapid FiO_2 optimization) vs. those who do not receive the study intervention] at either interim analysis. A clinician can withdraw a subject from the study for worsening clinical status including worsening respiratory status (based on clinical judgment, arterial blood gas analysis, or increasing FiO_2 requirement). The site PIs at each collaborating institution will be responsible for reporting all predefined SAEs, as well as any other adverse events felt to be related to the study protocol, to the coordinating site, Cooper University Hospital. In addition to reporting all adverse events to the DSMB, all adverse events will be submitted to each institution's IRB for review.

Registration: This study will be registered on clinicaltrials.gov

References

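### Between-group tests and the 15% SAE definition are grouped by receipt of the intervention, not by consent into REOX II, and deaths before consent are not counted

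*Combined protocol and SAP*

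**What the plan says.** The combined protocol and SAP defines the two groups in two ways.

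- **By phase.** D.1.2 Overview describes the design as "REOX II (intervention component) versus REOX I (observational component" and plans 205 and 75 subjects. It also states "Primary outcome: Good neurological outcome", meaning mRS ≤3 at hospital discharge.
- **By receipt.** The Secondary analyses paragraph tests that same outcome between subjects who get rapid FiO2 optimization "vs. those who do not receive the study intervention, using binomial test". The 180-day cognitive scores, return to work and plasma IsoPs/IsoFs use the same two groups. The safety monitoring section sets its 15% SAE comparison between subjects who receive the intervention "vs. those who do not receive the study intervention] at either interim analysis". Death and withdrawal for any reason are both listed SAEs.

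D.2 sets out how a subject reaches each group. The intervention needs written surrogate consent within four hours of ROSC. The observational route stays open "for subjects who are excluded from the study intervention due to lack of informed consent within the first four hours after ROSC"; for them, "we will approach subjects or surrogates at a later time for written informed consent and HIPAA authorization for participation in the observational component". Once consent is given, the on-call investigator "will ensure activation and adherence to the clinical protocol". The safety section allows a clinician to withdraw a subject whose condition worsens, but gives no rule for that subject's analysis group.

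The Sample Size paragraph adds: "We have enrolled 200 subjects in REOX I to date".

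**The concern.** Two features deserve attention.

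First, a grouping by receipt depends on what happens after enrolment. A consented subject in whom the protocol is never activated, for example because of early deterioration, is on the literal wording a non-recipient. Such subjects would tend to have poor outcomes. Moving them to the other side would flatter the intervention in the mRS comparison and shift their SAEs to the comparator.

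Second, membership of the intervention group requires being alive, with a reachable surrogate, when consent is given. REOX II-era subjects who fail that condition may enter the comparator later. No visible text says how deaths before consent are counted in either phase, and no table or sensitivity analysis is planned for them.

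At stake are the only visible test of the outcome that the Overview calls primary, and the only numeric safety comparison put to the DSMB. As written, these between-group comparisons are unadjusted binomial, t or Mann-Whitney tests, so nothing in them would offset a selection effect.

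**Working it through.** **Plan figures.** None bears directly on this point. The sample-size chain (85 × 1.15 = 97.75, so 98; 98/0.35 = 280) serves the regression models and does not depend on the grouping. The planned sizes agree: 205 + 75 = 280. With 200 already in REOX I, 5 places remain in its planned 205.

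**Inputs from the documents.** Group sizes 75 and 205; the first interim look at 25 REOX II subjects; 200 REOX I subjects to date; the 15% threshold, read here as percentage points.

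**Assumed inputs.** Good outcome 30% with no true effect (the plan expects 35% discharged with mRS ≤4 and tested at 180 days, so 30% at ≤3 is plausible). Mortality 60% (the cited ICU cohorts report 45-63%). The share dying before consent, the share consented but not activated, and the 10% good outcome in atypical subjects have no basis in the documents and are illustrative.

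**Yardstick.** SE of the difference = √[0.30 × 0.70 × (1/75 + 1/205)] = 6.2 points.

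**1. Receipt versus consent.** Let a share of the 75, with 10% good outcome, be counted as non-recipients. All 75 together have 22.5 good outcomes and the 205 have 61.5.

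- 5% (3.75 subjects): 22.125/71.25 = 31.1% versus 61.875/208.75 = 29.6%, a gap of +1.4 points.
- 10% (7.5 subjects): 21.75/67.5 = 32.2% versus 62.25/212.5 = 29.3%, a gap of +2.9 points.
- Grouped by consent, the gap is 0 in both cases.

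**2. Subjects diverted to the comparator.** With 10% good outcome among them:

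- 5 subjects: (200 × 0.30 + 5 × 0.10)/205 = 29.5%, a shift of 0.5 points.
- 30 subjects: (200 × 0.30 + 30 × 0.10)/230 = 27.4%, a shift of 2.6 points.

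**3. Deaths before consent.** Let the intervention group lose a share x of all ROSC subjects this way, and the comparator a share y. Good outcome is then 0.30/(1−x) versus 0.30/(1−y). The false-positive rate comes from exact enumeration of a pooled two-sided 5% z test at 75 versus 205, standing in for the binomial test.

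| x | y | Gap (points) | False-positive rate |
|---|---|---|---|
| 0 | 0 | 0 | 5.0% |
| 2% | 0 | +0.6 | 5.2% |
| 5% | 0 | +1.6 | 6.0% |
| 10% | 0 | +3.3 | 8.7% |
| equal | equal | 0 | about 5% |
| 2% | 10% | −2.7 | 7.0% |

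**4. SAE comparison for death.** This is the probability that the observed excess tops 15 points at 25 versus 200, given a true 20-point excess.

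- No early-death selection: 71.5%.
- x = 2/5/10%, y = 0, excess added to mortality among those treated, (0.60−x)/(1−x) + 0.20: 68/63/53%.
- Same x and y, excess added among all with ROSC, (0.80−x)/(1−x): 70/67/62%.
- x = 2%, y = 10%, comparator mortality (0.60−0.10)/0.90: 83-84%.

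**5. Would a four-hour landmark settle it?** Not fully. With 5% of each group dead by four hours, both stand at 0.30/0.95 = 31.6%. If REOX I alone then loses 2% or 5% of the remainder before later consent, it rises to 32.2% or 33.2%, a gap of −0.6 or −1.7 points.

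**The case against.** The strongest reply is that the wording is shorthand. Therapeutic interventions says that subjects enrolled in the intervention will be given the protocol, that those without timely consent will not have it activated, and that an investigator sees to activation. The Overview labels REOX II the intervention component. Read together, enrolled, receiving and REOX II are almost the same set. This largely stands: it confines misclassification to consented subjects who are never activated or are withdrawn before activation. It does not supply a rule for them.

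Four stronger readings are tempting, and the documents do not support them.

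- *Withdrawn subjects are moved to the comparator.* The safety section lets a clinician withdraw a subject from the study; it does not say where that subject is analysed. The transfer is only an inference from the receipt wording.
- *Survival to consent biases the result in favour of the protocol.* That needs the comparator to keep early deaths that the intervention group loses. REOX I participation also requires later consent, so early deaths may drop out of both. Figure 9, the REOX I protocol and the DSMB Charter are not visible.
- *A stopping rule is disabled.* The 15% figure defines an excessive rate; no automatic action is attached. The DSMB judges the whole safety profile, unmasked, and reviews every SAE report, including withdrawals.
- *The main analysis is compromised.* The adjusted models use TWA-PaO2 as the exposure, not group, and the sample size serves the multivariable models. The affected tests are headed secondary, although the Overview names mRS ≤3 as primary.

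**Conclusion.** The point holds as a matter of definition and reporting, and should be fixed. The between-group tests and the SAE comparison are defined by receipt while the design is defined by phase, and no rule covers the subjects for whom these differ. That part is worth about 1.4-2.9 points if 5-10% of the 75 are never activated, a share that the plan's own procedures make unlikely.

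The selection through timely consent and survival to consent is a separate matter. Under the assumed rates it ranges from −2.7 to +3.3 points for early deaths. Diverted subjects shift the comparator by 0.5 points if 5 fill the planned 205, and by 2.6 if there are 30. All of this is modest against a standard error of 6.2 points, and neither its actual size nor its sign can be read from the visible documents. That is a reason to count these subjects, not evidence that the comparison is biased in a known direction. The TWA-PaO2 models are unaffected.

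**What to change.** 1. In Secondary analyses and in the safety monitoring section, define the groups as all subjects consented into REOX II, whatever was delivered or later withdrawn, versus REOX I. Keep every death and withdrawal after consent in the REOX II group for the SAE comparison. Align the DSMB Charter if it sets denominators.
2. Flag concurrent REOX I subjects who lacked timely consent, and report the between-group results with and without them.
3. Tabulate deaths before consent in both phases, by time from ROSC, and show the table to the DSMB.

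A four-hour landmark analysis of mRS is optional and needs care. Consent and activation can come well before four hours, so restricting to subjects alive then drops deaths after activation and could hide early harm. If used, it should be a labelled sensitivity analysis, never applied to the safety comparison, and reported with the number of REOX II subjects who died after activation but before four hours. The report should state that it conditions on a post-treatment event and does not remove selection on surrogate availability or later consent.

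Item 1 removes only the receipt-grouping problem; items 2 and 3 expose the remaining selection but do not remove it. The cost is a change of wording, one flag, one table and one repeated set of comparisons. The documents do not state that time of death is recorded, so it may need to be added to data collection. Grouping by consent dilutes slightly: with 5-10% untreated, a 10-point effect becomes 10 × 0.95 = 9.5 to 10 × 0.90 = 9.0 points.

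### Both binary comparisons between protocol and no-protocol patients are assigned a binomial test, which is a one-sample test; a two-sample test should be named, because the literal reading raises type I error to about 7–9% for mRS ≤3.

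*Combined protocol and SAP*

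**What the plan says.** In the combined protocol and SAP, the secondary-analyses paragraph of the Analysis section compares the proportion with mRS ≤3 in patients given rapid FiO₂ optimization "vs. those who do not receive the study intervention, using binomial test". For the 180-day functional outcome it says: "We will compare the proportions of patients able to return to work between the two groups using binomial test". It gives no reference proportion, alpha or sidedness for either test. For the continuous outcomes the same paragraph names t-tests or Mann-Whitney U, which are two-sample procedures.

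Section D.1.2 (Overview) gives the group sizes as "280 patients (205 from REOX I and 75 from REOX II" and ranks the first of these outcomes highest: "Primary outcome: Good neurological outcome (defined as Modified Rankin Scale ≤ 3". The main modelling text takes a different route. It regresses mRS, treated as continuous, on time-weighted PaO₂ with covariates. The binomial-test sentence is therefore the only test in the document that compares mRS ≤3 between patients who do and do not get the intervention.

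**The concern.** A binomial test asks whether one group's count is compatible with a proportion fixed in advance. Here the other proportion is also a sample estimate, from roughly 205 patients for mRS ≤3 and from far fewer survivors for return to work. An analyst who follows the wording literally must supply a null proportion, and the natural candidate is the comparator's observed rate. The sampling error of that rate then drops out of the calculation. P-values come out too small and intervals too narrow, on an outcome that the Overview calls primary. The problem would exist even if the two groups were exchangeable, so it is separate from the lack of randomisation and of covariate adjustment in this comparison.

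**Working it through.** **The plan's own figures.** None is given for the binary comparisons. The sample-size paragraph concerns the cognitive regressions, and it reproduces. An overall test of R² = 0.15 with six predictors at alpha 0.05 needs 84 subjects for 80% power (the plan says 85). Then 85 × 1.15 = 97.75, or 98, and 98 / 0.35 = 280. None of this bears on the binary tests.

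**Inputs.** Group sizes of 75 and 205 come from the Overview. The 205 is approximate, because patients who miss the four-hour consent window join the observational group. The true mRS ≤3 rate is not given (the 35% in the plan refers to mRS ≤4), so I assume 15–50%. A two-sided 5% level is also assumed; the plan states alpha only for the regression ("In order to achieve 80% power and an $\alpha = 0.05$ we would require a minimal of 85 subjects").

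Return-to-work group sizes are not given. Taking 35% of each group gives 75 × 0.35 ≈ 26 and 205 × 0.35 ≈ 72. Applying the plan's 15% loss as well gives 75 × 0.35 × 0.85 ≈ 22 and 205 × 0.35 × 0.85 ≈ 61.

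**Normal approximation.** With equal true rates p, the difference has variance p(1−p)(1/75 + 1/205). The one-sample test uses only p(1−p)/75. The ratio is 1 + 75/205 = 1.366, with square root 1.169. The actual error rate is 2 × [1 − Φ(1.96 / 1.169)] = 0.094.

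**Exact enumeration.** I summed over all outcomes of two independent binomials with equal true rates of 15–50%. The smaller group was tested against the larger group's observed rate, with the two usual two-sided exact p-values.

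| Comparison | One-sample, minimum-likelihood p | One-sample, doubled-tail p | Two-sample chi-square |
|---|---|---|---|
| mRS ≤3, 75 vs 205 | 8.2–9.1% | 7.1–7.7% | 4.8–5.1% |
| Return to work, 26 vs 72 | 8.1–8.6% | 5.9–6.7% | 4.8–5.2% |
| Return to work, 22 vs 61 | 7.5–8.1% | 5.8–6.6% | 4.7–5.3% |

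Fisher's exact test gives 4.0–4.3% at 75 vs 205 and 3.3–3.9% at 26 vs 72.

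**One illustrative data set.** Take 31/75 (41.3%) against 62/205 (30.2%). The one-sample test gives p = 0.044 by minimum likelihood and p = 0.054 by doubled tail. The two-sample chi-square gives p = 0.081 and Fisher's test p = 0.087. The one-sample p-value is well below the two-sample one in both variants, but it crosses 0.05 in only one of them.

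**Interval width at an assumed 30% rate.** One-sample: 1.96 × √(0.21/75) = 10.4 points. Two-sample: 1.96 × √[0.21 × (1/75 + 1/205)] = 12.1 points.

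**The case against.** The best reply is that this is loose naming. The plan speaks of comparing proportions between two groups, fixes neither group's rate, and uses two-sample tests in the neighbouring sentences. A one-sample test cannot even be run without a null value, and none is supplied. On that reading the authors meant a two-sample test of proportions and nothing is inflated. This stands: the excess error is conditional on the literal reading. It does not rescue the wording, because the named procedure is then the wrong name for the intended one, and the p-value is left to the analyst's interpretation.

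It is also fair that both comparisons are listed as secondary, and that the covariate-adjusted regressions and the sample size built on the cognitive ones are untouched. That limits the weight of the point.

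Two stronger readings are tempting, and the documents support neither. A reader might infer a false-positive rate of about 31%. That needs the roles reversed, with the 75 intervention patients' rate treated as known and the 205 comparators tested against it, and nothing in the plan suggests this. A reader might also infer that the plan breaks a promised alpha. The 0.05 is attached only to the regression sample size, so no promise is made for these tests.

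**Conclusion.** The test named for both binary comparisons is wrong as written. Applied literally, with the comparator's observed rate as the fixed reference, it gives a type I error of about 7–9% for mRS ≤3 and about 6–9% for return to work, where a two-sample chi-square gives about 5%. If a two-sample test was intended, the error rate is sound and only the name is wrong. The figures rest on an assumed two-sided 5% level, true rates of 15–50%, a comparator of about 205, and derived group sizes for return to work. I rate this a moderate correction. The Overview's label for mRS ≤3 makes it worth making, while the secondary status of both comparisons and the benign alternative reading keep it from being critical. It does not address the confounding in a non-randomised, unadjusted comparison.

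**What to change.** In both sentences, replace the binomial test with a named two-sample test: for example, chi-square for mRS ≤3 and Fisher's exact test for return to work, where the groups are small. State that the tests are two-sided and give the alpha. Report each result as a risk difference with a two-sample 95% confidence interval, such as Newcombe or Miettinen-Nurminen; the choice between these is a matter of preference.

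The cost is one line of wording, with no extra patients or data. Compared with the literal one-sample reading, the interval for mRS ≤3 widens to the half-width of about 12.1 points shown above, which is the uncertainty that these group sizes actually carry. Fisher's test is somewhat conservative at the return-to-work sizes.
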